10.3.1	Treatment Comparisons	18
10.3.2	Primary Hypothesis	18
10.4	SAFETY ANALYSIS	19
10.4.1	Adverse Events	19
10.4.2	Clinical Laboratory Data	19
10.4.3	Other Safety Evaluations	19
11.	RECORDING AND COLLECTION OF DATA	19
11.1	CASE REPORT FORM	19
11.2	STUDY FILES AND SUBJECT SOURCE DOCUMENTS	20
11.3	MONITORING	20
11.4	AUDIT	20
11.5	RETENTION OF DATA	21
12.	PUBLICATION POLICY AND SHARING OF DATA.....	21
ATTACHMENT A: Schedule of Assessments		22
ATTACHMENT B: Summary of Changes		23

Study Synopsis

Sponsor	Vergent Bioscience, Inc. [REDACTED]
Title	A Phase 2, Multi-center, Open-label Study to Evaluate the Safety and Efficacy of VGT-309, a Tumor-Targeted, Activatable Fluorescent Imaging Agent, in Subjects Undergoing Surgery for Cancer in the Lung
Protocol Number	VGT-309-2B-2023
Lead Clinical Investigator	[REDACTED]
Study Centers	Up to 7 Centers in the US and Australia
Investigational Medicinal Product (IMP) (also referred to as Study Drug)	VGT-309 for Injection, 10 mg/vial
Primary Efficacy Objective	Assess the efficacy of VGT-309 with near-infrared (NIR) imaging for lesion visualization when compared to standard surgical techniques in subjects undergoing surgery for proven or suspected cancer in the lung.
Secondary Efficacy Objective	Assess the utility of VGT-309 with NIR imaging to identify cancerous tissue as confirmed by histopathology.
Safety Objective	Determine the safety and tolerability of VGT-309 in subjects with proven or suspected cancer in the lung.
Introduction and Rationale	[REDACTED]

Primary Endpoint - Efficacy	
Identify the proportion of subjects with at least one Clinically Significant Event (CSE) as defined by:
 
 Intraoperative localization of one or more preoperatively identified lung lesions using VGT-309 with NIR imaging when standard surgical techniques using white light and/or palpation failed to identify the lesion(s), and lesion(s) are confirmed by histologic examination to be other than normal lung tissue. Identification of one or more synchronous or occult lung lesions using VGT-309 with NIR imaging when standard surgical techniques using white light and/or palpation and preoperative imaging failed to identify the lesion(s), and lesion(s) are confirmed by histologic examination to be cancerous or precancerous. Identification of fluorescence within ≤ 10 mm from the inside edge of the closest staple line as measured by the investigator ex vivo in the operating room using NIR imaging, with pathologic margin confirmed by histologic examination to be ≤ 10 mm. NOTE: Margins from excisions of known or suspected metastases at the time of the surgery, OR diagnostic wedge resections where a completion lobectomy or segmentectomy was subsequently performed, will not be considered for Margin CSE inclusion. Identification of lymph nodes by VGT-309 with NIR imaging confirmed by histologic examination to be cancerous.
Safety Endpoints	Assessment of clinical laboratory tests, physical exam results, ECGs and vital sign measurements at various time points during the study, and documentation of treatment-emergent adverse events.
Secondary Endpoints - Efficacy	
To evaluate the sensitivity, positive predictive value (PPV), and 1-PPV of VGT-309 with NIR imaging for lesion(s) in vivo:
 
 Sensitivity is defined as the probability that the tissue fluoresces when it is cancer, as confirmed by histology $(TP/(TP+FN))$ * Positive predictive value (PPV) is defined as the probability that a tissue sample contains cancer on histologic exam if it fluoresces $((TP/(TP+FP))$ 1-Positive predictive value (1-PPV) is defined as the probability that a tissue sample does not contain cancer when it fluoresces $((FP/(TP+FP))*$ 
* TP = true positive, FP = false positive, FN = false negative

	
Inclusion Criteria	
In order to be enrolled in the study the subject must:
 
 Be willing and able to sign the informed consent and comply with study procedures. Be at least 18 years of age.

	
3. Meet the following conditions:
 
 Female participants must be of non-childbearing potential, or, If of childbearing potential, be non-pregnant or non-lactating and agree to use highly effective contraception from screening through Day 30 after treatment. Male participants, if not surgically sterilized, and if engaging in sexual intercourse with a female partner of childbearing potential, must be willing to use highly effective contraception from screening through 30 days after treatment and agree not to donate semen during this waiting period. Highly effective contraception involves the use of a condom for the male, plus one of the following for the female: 
 Oral, injectable, implantable, intravaginal, or transdermal hormonal contraceptives, or Intrauterine device or intrauterine hormone-releasing system NOTE: Subjects who abstain from heterosexual intercourse as their usual and preferred lifestyle, will not be required to use contraception as described above. They are required to maintain abstinence from screening through Day 30 after treatment. Note: Subjects in a same sex relationship, must use a barrier form of contraception (e.g., condom, diaphragm) to protect against the transfer of the study drug in any bodily fluids. 
4. Have a lung nodule or mass that might be considered primary lung cancer or lung metastases whether or not it is biopsy-proven before surgery.
 
5. Be scheduled to undergo standard of care surgical resection for a lung nodule or mass with diagnostic and/or curative intent
 
6. Have acceptable kidney and liver functions at study entry as evidenced by:
 
 $ALT/AST \leq 1.5$ times the upper limit of normal Calculated Creatinine Clearance (CrCl) ≥ 50 ml/min (manual calculation using Cockcroft-Gault equation) Total bilirubin ≤ 1.5 times the upper limit of normal 
7. Have an ECOG score of 0-2.
 
8. Meet all standard of care surgical and general anesthesia requirements.
 
9. Have not participated in an interventional clinical trial within the last 30 days (participation in a disease registry or quality of life study is not exclusionary).

Exclusion Criteria	
The subject may not be enrolled in the study if:
 
 They are not a candidate for standard of care surgery based on opinion of the surgeon, anesthesiologist, or other consulting physician. They have a known allergy or reaction to ICG, other radiographic contrast agent, or any component of VGT-309. They have congenital long QT syndrome or QTcF > 470ms by history or at Screening ECG. They have received chemotherapy or immunotherapy within 4 weeks prior to study enrollment. They are prisoners, institutionalized individuals, or are unable to consent for themselves. They have any other co-morbidity or habit that the Investigator believes will interfere with their ability to comply with and complete the study.

Study Methodology and Design	
This is a Phase 2, multi-center, open-label study to evaluate the safety and efficacy of VGT-309, a tumor-targeted, activatable fluorescent imaging agent, to identify cancer using NIR imaging in subjects undergoing surgery for proven or suspected cancer in the lung. Approximately 100 subjects will be enrolled to ensure at least 86 subjects are evaluable with the option to expand enrollment by protocol amendment if deemed necessary by the DSC to meet primary and/or secondary objectives.
 
Following agreement with and signing of the informed consent, subjects will undergo screening measurements for the study within 4 weeks prior to the anticipated dosing:
 
 1. Medical, surgical and medication history. 2. Complete physical exam, including vital signs and height. 3. Weight (needed for dose calculation) 4. Chemistry, hematology, coagulation and urinalysis with microscopy clinical laboratory studies. 5. 12-lead ECG. 6. Serum pregnancy test for females of child-bearing potential. 
[REDACTED]
 
[REDACTED]
 
Following surgery, subjects will be monitored for safety during their hospitalization. Between 7 to 14 days and 25 to 35 days after surgery, the subjects will return to the clinic or have a telehealth visit for safety assessments. At the last visit, if there are no adverse events requiring further follow up, subjects will then be released from the study.
 
If a subject chooses to withdraw from the study prior to the final visit, they will be asked to undergo a final safety assessment before their departure.

VGT-309 Description	[REDACTED]
VGT-309 Dosing	
The dose for this study is 0.32 mg/kg of VGT-309 and [REDACTED]. Based on ongoing investigations and after review by the DSC this dose may be modified.
 
[REDACTED]

Data Safety Committee (DSC)	
A Data Safety Committee will be appointed by Vergent Bioscience and will include at a minimum:
 
[REDACTED]

Enrollment Period	It is expected that the time required to enroll 100 subjects in this study will be approximately 8 months.
Study Duration	Each subject may expect to be on study for up to 65 days: 

Primary Efficacy Assessments	
In vivo, intra-operatively:
 
 • Use of white light and/or palpation followed by NIR imaging for localization of preoperatively identified lung lesion(s), potential synchronous or occult malignant lung lesion(s), and potential cancer-containing lymph nodes. 
Ex vivo, in the operating room:
 
 • NIR imaging to determine fluorescence proximity to closest resection margin. 
Ex vivo pathology
 
 • Histologic examination of resected tissues.
Secondary Efficacy Assessments	Comparison of NIR imaging, conducted both inside and outside the subject, to results of histologic examination.
Safety Assessments	
 • Treatment-emergent adverse events • Clinical laboratory assessments of blood and urine (See section 9.2.3 for details): 
 ○ Hematology Panel ○ Coagulation – INR and aPTT ○ Chemistry Panel including liver function tests (LFTs) and amylase ○ Urinalysis with microscopy • Pre- and post-dose ECGs (in triplicate) • Vital signs (BP, HR, temp, resp) • Additional studies if identified during the trial as being necessary to adequately assess safety

	
Pregnancies that occur between dosing and Day 30 will be followed until 6 weeks after delivery or termination of the pregnancy.
 
(Refer to Schedule of Assessments for details)

Statistical Methods	
Sample Size:
 
For the primary efficacy endpoint of proportion of subjects with at least one CSE, assuming a 20% true rate of at least one CSE, two-sided 5% Type 1 error and 80% power, the sample size to rule out a CSE rate less than or equal to 10% requires 86 evaluable subjects in the primary analysis group. The trial will have met the primary endpoint if at least 15/86 (17.4%) subjects have at least one CSE. The 95% two-sided Clopper-Pearson exact confidence bound at 17.4% is (10.1%, 27.1%).
 
Efficacy
 
A descriptive analysis of the baseline subject and tumor characteristics will be performed. Quantitative data will be presented as a standard set of summary statistics (n/mean (standard deviation)/median/minimum/maximum). Categorical data will be expressed as frequency (%).
 
For the primary endpoint analysis, the proportion of subjects undergoing NIR imaging with at least 1 CSE will be identified and tested under the following null hypothesis:
 
Ho: $P \leq 0.10$
 
The alternative hypothesis states that the proportion of subjects undergoing NIR imaging with at least 1 CSE will be greater than the chosen margin of 0.10:
 
Ha: $P > 0.10$
 
At 86 evaluable subjects, this trial is power at 80% to reject the null hypothesis of a 10% or fewer of subjects experiencing at least one CSE. Two-sided 95% exact confidence intervals for the proportion of subjects with at least one CSE will be constructed.
 
For the secondary endpoint analysis sensitivity, PPV, and 1-PPV will be calculated and presented along with 95% confidence intervals using GEE model analysis to factor in within-subject correlation for subjects with multiple tumors.
 
Safety:
 
Adverse event (AE) data will be listed by subject. Treatment-emergent adverse events (TEAEs), serious adverse events (SAEs), and AEs leading to study drug discontinuation will be summarized by system organ class and preferred term using the current version of the Medical Dictionary for Regulatory Activities (MedDRA).
 
Listings of individual subject laboratory results will be provided. Laboratory results, Clinically Significant and change from baseline for selected lab tests will be summarized by treatment at scheduled visits.
 
Twelve-lead ECGs and vital signs measurements will be listed by subject and summarized by incidence of events/abnormalities or descriptive statistics as appropriate. Individual data for physical examination findings, prior and concomitant medications and medical history will be provided.


List of Abbreviations:

AE	Adverse Event
ALP	Alkaline Phosphatase
ALT	Alanine Aminotransferase
APTT	Activated Partial Thromboplastin Time
AR	Adverse Reaction
AST	Aspartate Aminotransferase
BP	Blood Pressure
BUN	Blood Urea Nitrogen
CFR	Code of Federal Regulations
CT	Computed Tomography
eCRF	Electronic Case Report Form
CTCAE	Common Terminology Criteria for Adverse Events
DSC	Data Safety Committee
ECG	Electrocardiogram
EDC	Electronic Data Capture
FDA	Food and Drug Administration
GEE	Generalized Estimating Equation
GCP	Good Clinical Practice
GGT	Gamma-glutamyl-transferase
GLP	Good Laboratory Practice
GMP	Good Manufacturing Practice
Hgb	Hemoglobin
HREC	Human Research Ethics Committee
IB	Investigator's Brochure
ICF	Informed Consent Form
ICH	International Conference on Harmonization
INR	International Normalized Ratio
IRB	Institutional Review Board
ITT	Intent-to-treat
IV	Intravenous
kg	kilogram
L	Liter
LDH	Lactate Dehydrogenase
LFT	Liver Function Test
MedDRA	Medical Dictionary for Regulatory Activities
mg	milligram
mL	Milliliter
NIR	Near-infrared (imaging)
NOAEL	No-Observed-Adverse-Effect-Level
PI	Principal Investigator
PICF	Patient Informed Consent Form
PK	Pharmacokinetic
RBC	Red Blood Cell
ROC	Receiver Operating Characteristic
SAE	Serious Adverse Event
SD	Sprague-Dawley (rats)
SUSAR	Suspected Unexpected Serious Adverse Reaction

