10.3.2 Primary Hypothesis

The primary study hypothesis is that VGT-309 with NIR imaging is superior to white light and/or palpation for the intraoperative localization of preoperatively identified lung lesions.

The null hypothesis for the primary endpoint is that $\leq 10\%$ of subjects will have at least one CSE, while the alternative hypothesis is that proportion of subjects with at least one CSE will exceeds 10% as demonstrated by at least 15/86 (17.4%) evaluable subjects with at least one CSE.

For the primary endpoint analysis, the proportion of subjects with at least 1 CSE will be tested under the null hypothesis that this proportion is $\leq 10\%$.

$$H_0: p \leq 10\%$$

The alternative hypothesis states that the proportion of evaluable subjects with at least 1 CSE will be greater than 10%:

$$H_a: p > 10\%$$

The primary analysis will use the EP population. This analysis may be repeated using the ITT population. One-sided 2.5% exact binomial test will be used to test the null hypothesis. Clopper-Pearson exact two-sided 95% confidence intervals will be reported.

For the secondary endpoint analysis sensitivity, PPV, and 1-PPV will be calculated and presented along with 95% confidence intervals using GEE model analysis to factor in within-subject correlation for subjects with multiple tumors.

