## 9.3. Analysis of the Primary Efficacy Endpoint

Efficacy analyses will be performed on the Evaluable population. This analysis will be repeated using the ITT population. Quantitative data will be presented as a standard set of summary statistics (n, mean, standard deviation, median, minimum, and maximum values). Categorical data will be expressed as frequency (%).

A one-sided exact binomial test will be used to test the null hypothesis using a one-sided alpha of .025, and Clopper-Pearson exact two-sided 95% confidence intervals will be reported. A right-sided p value will be provided, which is the probability of finding the observed number of successes (subjects with at least 1 CSE) or a larger number, given that the null hypothesis is true.

Frequency of CSEs will also be summarized by CSE type across subject characteristics including the following categories:

- Age
- Smoking history
- Overall cancer stage – pre-operative

- Overall cancer stage – post-operative
- Surgery type
- Primary lung cancer type
- Prior cancer treatment
- Imaging system
- Resection type
- Lesion type by histopathology

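### With 86 evaluable subjects and the planned exact test, power at a 20% CSE rate is 76.3%, not the stated 80%

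*Protocol*

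**What the plan says.** The sample-size paragraph in the protocol synopsis (Statistical Methods) sets the design by "assuming a 20% true rate of at least one CSE" with "two-sided 5% Type 1 error and 80% power", and concludes that excluding a rate of 10% or below "requires 86 evaluable subjects in the primary analysis group". It gives the success rule: "The trial will have met the primary endpoint if at least 15/86 (17.4%) subjects have at least one CSE". It quotes a Clopper-Pearson interval of 10.1% to 27.1% at that result. The efficacy paragraph then repeats the power claim: "At 86 evaluable subjects, this trial is power at 80% to reject the null hypothesis".

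The test is fixed elsewhere. Protocol 10.3.2 says "One-sided 2.5% exact binomial test will be used to test the null hypothesis", with the Evaluable Population (EP) as the primary analysis set. SAP 9.3 says "A one-sided exact binomial test will be used to test the null hypothesis using a one-sided alpha of .025". Protocol 10.3.1 puts the same criterion as a lower 95% confidence bound above 10%.

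The protocol (synopsis and 5.1) and SAP section 4 plan about 100 enrolled so that at least 86 are evaluable. No readable text names the formula behind 86: Protocol 10.1 shows only its heading, and SAP section 5 is redacted.

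**The concern.** A binomial count is discrete, so an exact test at a nominal 2.5% usually spends less than 2.5%, and its power can fall short of a figure taken from a continuous approximation. The protocol gives everything needed to check this: the size, the success count, the null rate and the assumed rate. If the 80% came from an approximation while the analysis uses the exact test, the protocol claims more power than its own rule has.

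This is the trial's only confirmatory test. Anyone judging whether 86 subjects are enough, or later interpreting a narrow miss, would rely on a false-negative risk of 20% that the design does not have. Because the plan is for at least 86 evaluable subjects, it also matters what the power and the critical count become at the sizes the trial may actually reach.

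**Working it through.** **Inputs.** Null rate p0 = 0.10, assumed rate p1 = 0.20, two-sided 5% (2.5% in the upper tail), target power 80%, n = 86 and success at 15 or more, all from the protocol synopsis. Exact binomial test at one-sided 2.5%, from Protocol 10.3.2 and SAP 9.3.

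**1. Reproducing 86.** The uncorrected one-sample normal approximation gives

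n = [1.96 × √(0.10 × 0.90) + 0.8416 × √(0.20 × 0.80)]² / (0.20 − 0.10)²
= [0.5880 + 0.3366]² / 0.01 = 85.5, rounded up to 86.

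Its approximate power at 86 is Φ[(0.10 × √86 − 0.5880) / 0.40] = Φ(0.848) = 80.2%. Other standard formulas at the same alpha and power do not give 86: 95.2 with continuity correction, 97.5 by arcsine, 125.6 with the alternative variance only, and 70.6 with the null variance only.

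**2. Reproducing the success rule.** With X ~ Binomial(86, 0.10):

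- P(X ≥ 14) = 0.0461, above 0.025
- P(X ≥ 15) = 0.0230, below 0.025

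So 15 is the exact critical count at 86. The Clopper-Pearson interval at 15/86 is 10.1% to 27.1%, as stated.

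**3. Power of that rule.** With X ~ Binomial(86, 0.20):

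P(X ≥ 15) = 0.7626, i.e. 76.3%.

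The shortfall is 80 − 76.3 = 3.7 percentage points, and the miss probability is 100 − 76.3 = 23.7%. For the 15/86 rule to have 80% power, the true rate would have to be about 20.6%.

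**4. Whether another test gives 80%.** At n = 86 the score test, with or without continuity correction, also needs 15 events (76.3%). The Wald test needs 16 (66.9%). A one-sided 5% exact test needs 14 and has 84.1% power, but that contradicts both the stated alpha and the 15/86 rule.

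**5. Other evaluable sizes.** Recomputing the critical count at each size under the exact one-sided 2.5% test:

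| Evaluable n | Critical count | Exact one-sided alpha | Power at 20% |
|---|---|---|---|
| 86 | 15 | 0.0230 | 76.3% |
| 87 | 16 | 0.0120 | 68.7% |
| 90 | 16 | 0.0163 | 74.0% |
| 94 | 16 | 0.0239 | 80.1% |
| 95 | 17 | 0.0128 | 73.4% |
| 100 | 17 | 0.0206 | 80.8% |

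The critical count is 15 for 80–86, 16 for 87–94 and 17 for 95–102. Between 86 and 100, only 94 and 100 reach 80%. Power drops each time the count steps up (77.4% at 103, 79.6% at 110) and is at least 80% at every size only from 111.

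**6. The threshold read as a proportion.** Requiring an observed proportion of at least 15/86 (17.4%) gives the same count as the exact test at 87–91 and 95–97. At 92–94 it asks for 17 rather than 16, and at 98–102 for 18 rather than 17, so it is one event stricter there.

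**The case against.** The strongest reply is that the gap is small and nothing in the analysis depends on it. A shortfall of 3.7 points disappears if the true rate is 20.6% instead of 20%, a difference well within the uncertainty of any planning assumption. The test, its alpha, the critical count, the interval and the analysis population are all unaffected. This stands as a limit on the importance of the point, but it does not make the 80% statement true.

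A second reply is that about 100 will be enrolled, so the evaluable number may exceed 86. This helps only at some sizes: power at 87 or 95 is lower than at 86.

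A third is that the unreadable sample-size sections may name the method or call the power approximate. That is possible, and for this reason the normal-approximation origin of 86 is an inference. The 76.3% does not depend on it.

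A reader might also infer that 15 subjects with a CSE would count as success whatever the evaluable size. At 100 evaluable subjects that would give a one-sided type I error of 7.3%. The documents do not support this reading. The rule is written with its denominator; Protocol 10.3.1, Protocol 10.3.2 and SAP 9.3 all judge the result by the exact interval or test; SAP 9.2 states the hypotheses without the 15/86; and Protocol section 10 lets the SAP govern where the two differ. A result of 15 out of 100 would fail the planned test, so the type I error is protected.

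**Conclusion.** The point holds as a correction to the stated power. Under the protocol's own size, success count, null rate and assumed rate, the planned exact test has 76.3% power at exactly 86 evaluable subjects, and between about 69% and 81% over 86 to 100. This rests on independent subjects with a common CSE rate of 20%, and on the exact one-sided 2.5% test being the primary analysis, as both documents say.

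Two further conclusions that a reader might draw should not be drawn. The one-sided type I error is not inflated: the planned test keeps it at or below 2.5% at every size. Nor is 94 a safe replacement target: it is the smallest size reaching 80%, but power falls to 73.4% at 95.

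The 15/86 wording is a minor matter of alignment. It is correct at 86 and, if taken as a fixed 17.4%, errs only on the strict side at 92–94 and 98–102.

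**What to change.** In the protocol synopsis, and wherever the figure is repeated:

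- Restate the power as about 76% at 86 evaluable subjects under the one-sided 2.5% exact binomial test, for a true rate of 20% against 10%.
- Add that, with the critical count recomputed, exact power runs from about 69% to 81% over 86–100 evaluable subjects (68.7% at 87, 80.1% at 94, 73.4% at 95, 80.8% at 100), and is at least 80% at every size only from 111.
- If the 80% is kept anywhere, label it as a normal-approximation figure, provided the sponsor confirms that origin.

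To align with SAP 9.3, label 15/86 in the synopsis and in Protocol 10.3.2 as the critical count at exactly 86. State that success is judged by the exact test at the actual EP size: 15 events for 80–86, 16 for 87–94, 17 for 95–102.

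The cost is wording and a slightly less favourable stated power. No extra subjects are needed and the planned analysis does not change.

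### The stated 80% power at 86 evaluable subjects does not belong to the planned test: the exact rule of 15 or more out of 86 has 76.3% power at a 20% CSE rate

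*Protocol*

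**What the plan says.** The sample-size paragraph of the protocol synopsis sets out the design "assuming a 20% true rate of at least one CSE, two-sided 5% Type 1 error and 80% power", and concludes that "the sample size to rule out a CSE rate less than or equal to 10% requires 86 evaluable subjects". It then gives the decision rule: "The trial will have met the primary endpoint if at least 15/86 (17.4%) subjects have at least one CSE". It reports the Clopper-Pearson 95% interval at that count as 10.1% to 27.1%. The efficacy paragraph of the same synopsis section repeats the power claim: "At 86 evaluable subjects, this trial is power at 80% to reject the null hypothesis".

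The test itself is specified elsewhere. Protocol section 10.3.2 says "One-sided 2.5% exact binomial test will be used to test the null hypothesis" and repeats the threshold, "as demonstrated by at least 15/86 (17.4%) evaluable subjects with at least one CSE". SAP section 9.3 agrees: "A one-sided exact binomial test will be used to test the null hypothesis using a one-sided alpha of .025".

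The visible text names no formula for the sample size. Protocol section 10.1 shows no text under its heading, and SAP section 5 is redacted.

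**The concern.** Sample size, success threshold and assumed true rate are all printed, so the power is a single binomial tail probability and can be checked directly. It does not come to 80%. The figure of 86 looks like the output of a large-sample formula, whereas the analysis uses an exact test with a whole-number cut-off.

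Power is the figure on which the sponsor accepts a given risk of a failed primary endpoint. If it is overstated, that risk is understated. The plan also enrols about 100 subjects to obtain at least 86 evaluable, and lets the Data Safety Committee consider expansion to meet the objectives. Anyone making that decision should have the true operating characteristics.

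**Working it through.** **Inputs.** From the protocol synopsis: null rate p0 = 0.10, assumed rate p1 = 0.20, two-sided 5% (one-sided 2.5%), n = 86, success at X ≥ 15. From protocol section 10.3.2 and SAP section 9.3: exact binomial test, one-sided 2.5%.

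**Step 1: reproduce the plan's 86 and 80%.** The one-sample normal-approximation formula is

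n = [(z₀.₉₇₅·√(p0(1−p0)) + z₀.₈₀·√(p1(1−p1))) / (p1 − p0)]²

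= [(1.95996 × 0.3 + 0.84162 × 0.4) / 0.10]² = (0.92464 / 0.10)² = 85.5, rounded up to 86.

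Approximate power at 86 is Φ[(√86 × 0.10 − 1.95996 × 0.3) / 0.4] = Φ(0.848) = 80.2%. Both stated figures are recovered. Other common formulas at one-sided 2.5% do not give 86: the continuity-corrected version gives 96, the arcsine version 98, and the version using only the alternative variance 126.

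**Step 2: check the threshold and interval.**

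| Events needed of 86 | P(X ≥ r) at 10% | P(X ≥ r) at 20% |
|---|---|---|
| 14 | 0.0461 | 0.841 |
| 15 | 0.0230 | 0.763 |
| 16 | 0.0107 | 0.669 |

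Fifteen is the smallest count that keeps the one-sided error at or below 2.5%. The Clopper-Pearson interval at 15/86 is 10.1% to 27.1%, as printed.

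**Step 3: power of the printed rule.** P(X ≥ 15 | n = 86, p = 0.20) = 0.7626, or 76.3%. The shortfall is 80.0 − 76.3 = 3.7 points, and the type II error is 100 − 76.3 = 23.7%.

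**Step 4: why the approximation is too high.** On the count scale it puts the cut-off at 86 × (0.10 + 1.95996 × √(0.09/86)) = 14.05 events. A count must be whole, so the cut-off actually used is 15. An uncorrected z-test would do no better: z is 1.94 at 14 events and 2.30 at 15, so it also first rejects at 15. A mid-p test does the same (one-sided mid-p 0.0345 at 14, 0.0169 at 15). Power is 76.3% under all three.

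**Step 5: the rate at which 80% is reached.** Solving P(X ≥ 15 | 86, p) = 0.80 gives p = 0.2056.

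**Step 6: other evaluable counts.** The exact one-sided 2.5% test is applied at each n, with its own critical count, at a true rate of 20%.

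| Evaluable n | Events needed | Exact power |
|---|---|---|
| 86 | 15 | 76.3% |
| 87 | 16 | 68.7% |
| 90 | 16 | 74.0% |
| 94 | 16 | 80.1% |
| 95 | 17 | 73.4% |
| 100 | 17 | 80.8% |

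Between 86 and 100, only 94 and 100 reach 80%. The 15-event threshold applies at 86 and does not carry over: at n = 87, 15 events give one-sided p = 0.0253 and a lower confidence bound of 9.98%, so the test fails.

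**The case against.** The best defence is that nothing deciding the trial's conclusion is affected. The test, the threshold, the type I error of 0.0230 and the interval are right and mutually consistent, and power plays no part in the primary analysis. The gap is 3.7 points in a planning figure for a single-arm Phase 2 study. It rests on an assumed 20% rate for which the visible text gives no basis, and moving that rate by 0.6 points restores 80%. The figure is also not a slip of calculation, since a standard formula produces it. That this formula was used is an inference, and the hidden sample-size sections might already call the 80% approximate. Finally, the plan enrols above 86, and at 100 evaluable subjects exact power is 80.8%.

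Most of this stands as context. The consequence is modest, the validity of a positive result is untouched, and the origin of the 86 is inferred. None of it makes the statement true. The synopsis pairs 80% with 86 subjects and the 15/86 rule, and that rule has 76.3% power whatever formula led to 86. Text that is not visible could explain the figure but could not change the power of a rule printed in full. Enrolling above 86 does not reliably help either, because power is below 80% at most counts from 86 to 100. That range is illustrative: enrolment is approximate, and the protocol allows replacement and expansion.

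**Conclusion.** The concern holds. Under the plan's own test, threshold and assumed rate, power at 86 evaluable subjects is 76.3%, against a stated 80%. The chance of missing the primary endpoint at a true 20% rate is 23.7%, against an implied 20%; the relative increase of about 18% (3.7/20) is the same gap on another scale. The fault is a mismatch between what appears to be a normal-approximation sample size and an exact analysis. It overstates the chance of success and leaves the false-positive risk unaffected.

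The 76.3% needs only the printed inputs and independent subjects with a common CSE rate of 20%. The figures for other evaluable counts further assume that the exact test's critical count is recalculated at each n.

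**What to change.** Keep the design and correct the power statement in both places in the synopsis, and in protocol section 10.1 and SAP section 5 if they carry the same figure. Suggested text:

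> With 86 evaluable subjects and the exact one-sided 2.5% binomial test (success at 15 or more), power is 76% for a true CSE rate of 20% and 80% for a true rate of 20.6%.

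Add one line on other evaluable counts, for example:

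> For 86 to 100 evaluable subjects, with the critical count recalculated for each number, exact power at a 20% rate ranges from 68.7% (87 subjects, 16 needed) to 80.8% (100 subjects, 17 needed).

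The cost is wording, plus a stated figure that is slightly less favourable. No additional patients are requested, and the test, threshold and endpoint do not change.
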